The experimental, feedback version includes the standard plus feedback on RT and inhibition errors compared to pre-drinking (Fig. 3). Based on past findings⁴⁵⁻⁵¹, if they react >20 ms slower and/or make $>5\%$ errors, they will get a message summarizing the performance decrement and implications for an outcome, picked randomly among trouble driving, risky sex, drug use, delinquency, or aggression. The app will state that there are simple alternatives with invitation to press a box to view advice, based on research that risk information may increase risky behavior if convenient options are not given⁷². Feedback will be worded non-judgmentally per motivational interviewing tenets.

Post-session field use:

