
Follow-up appointment:

After 4 weeks, participants will come to our office for an updated TLFB and give usability and acceptability ratings for the CGNG experimental feedback app based on the 4-week field period. Staff will extract data from the phones, participants will be paid, and clinical referrals will be provided when appropriate. Participants who participate entirely remotely will complete their follow-up appointment via Password-Protected UF Zoom. Participants will receive \$30 for attending this appointment. They will receive all other earned compensation at this time via a prepaid debit card.

Six- & 12-month follow ups: At six and twelve-months post completion of the study, participants will be contacted via electronic mail and will be asked to complete a survey comprised of

previously approved measures and items regarding use of alcohol reduction smartphone apps and other means of alcohol use reduction. The survey will be completed through the secure website www.REDCap.com. Payment for completion of each survey will be \$25.

Assessments:

Web/phone screener:

Demographic information: This questionnaire assesses basic demographic information, including age, sex, weight, and whether they are a Foreign National or not.

Frequency and quantity of alcohol consumption: Three multiple choice items will be included, which will assess number of drinking days; number of heavy drinking days (5 or more for men, 4 or more for women) and peak number of drinks in a 24-hour period in the past 30 days.

Liking for different alcoholic beverages: An item will be included concerning participants' liking of beer, wine, vodka (straight or in mixer) and rum (straight or in mixer).

General questions regarding other inclusion criteria: Two questions will list several inclusion criteria and ask participants whether or not all of the listed criteria pertain to them. This will provide information regarding inclusion and exclusion to study staff while not requiring participants to provide specific information along these lines as part of the preliminary screen.

In-Person Screening Appointment:

Vital signs (i.e., blood pressure and pulse readings), *height and weight*.

Withdrawal: The *Clinical Institute Withdrawal Assessment for Alcohol (Revised) (CIWA-AR)*²⁹ will be used to assess withdrawal symptoms. The CIWA is a reliable 10-item instrument designed to assess severity of current withdrawal syndrome.

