Impaired control: The *Impaired Control Scale*³³ (*ICS*) consists of three parts including 5 items concerning actual attempts at limiting alcohol consumption (Part 1); 10 items assessing the frequency of past failures at controlling drinking (Part 2) and 10 items assessing beliefs regarding future ability to control drinking (Part 3). Parts 1 and 2 will be administered in this study. The ICS is reliable and has been validated in clinical and community samples. Items are rated on a 0 to 4 scale and summed with higher scores indicating greater difficulty in controlling consumption.

The *Protective Factors Questionnaire* measures frequency of alcohol-related protective strategy use on a 7-point scale. This measure has been used with young adult samples in several studies.

Facets of impulsivity: Impulsivity and risky decision making will be measured using the *UPPS Impulsive Behavior Scale*: a 59-item measure that assesses five subdimensions of impulsivity (premeditation, positive urgency, negative urgency, sensation seeking and perseverance). A *cued go/no-go task*⁶⁰ will be administered during the in-person screening appointment. This is a

8-10 minute computerized task which assesses the ability to inhibit a prepotent response. Subjects are instructed to press a key or inhibit pressing a key based on the colors of the shapes presented. The orientation of the shape (horizontal or vertical) before the color appears signals imperfectly the likelihood that the subsequent stimulus will be “go” or “no-go.” Participants receive feedback regarding their accuracy and speed of response.

In-Person Screening Appointment and at Preliminary Appointment Day of the Sessions:

Self-reported alcohol consumption and smoking: The *Timeline Followback Interview* (TLFB) will be administered at the in-person screening and updated at the preliminary appointment. Participants will be given a blank calendar including memory prompts (e.g., holidays), which covers the designated time interval (the prior 30 days at initial screening) and asked to reconstruct their drinking behavior and smoking over that interval. The TLFB has good test-retest reliability and good validity for verifiable events.

Marijuana use: Participants will be asked on how many days they have used any form or marijuana. Participants will be asked to report on the prior 30 days at the in-person screening appointment and since the in-person screening appointment at the appointment on the day of the session.

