Urine drug and pregnancy tests: Urine drug dips will be used to detect opiates, cocaine, phencyclidine, amphetamines, methamphetamine, barbiturates, methadone and benzodiazepines. Urine pregnancy tests will also be administered to all female participants. A positive test for any of the above drugs or a positive pregnancy test will lead to immediate exclusion from the study.

Symptoms: Adverse experiences are collected on standardized forms, using the *SAFTEE*. The SAFTEE includes 1) open-ended questions about any changes in physical or health problems, appearance, or activity level, and 2) yes/no responses to a specific list of symptoms for a specified time period. For each symptom reported on the SAFTEE a rater also records the severity (mild, moderate, or severe) and action taken.

Suicidality: The *Columbia Suicide Severity Rating Scale* (CSSRS) is a semi-structured interview that assesses past and current suicidal ideation, intent, and attempts. It will be used to monitor the safety of participants. Any participant reporting current suicidal ideation including intent to carry out a suicide attempt will be excluded from the study and the study physician, [name], will be alerted immediately.

Menstrual cycle data: Self-reports will be obtained from all women on their menstrual/gynecological status. We will include women who are cycling normally and/or on birth control pills. Three months of self-report data recording the start of their menses will be obtained prior to the alcohol drinking session. This information will be obtained initially at the in-person screening and updated at the pre-session screening appointment on the day of the alcohol self-administration session.

Brief Smoking Questionnaire: The Brief Smoking Questionnaire is a brief self-report survey that consists of four questions that evaluate current daily cigarette use and likelihood of nicotine dependence. I

Drinking Reduction Form: This is a brief survey consisting of three Yes/No questions. The first question determines whether a potential participant has used a smartphone app to reduce drinking in the previous 12 months. The next two questions determine whether a potential participant plans to take active steps to stop or cut down drinking in the next three months.

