Psychiatric symptoms/conditions: The 42-item *Depression Anxiety Stress Scale (DASS*⁸⁵) will be administered. This measure assesses several negative emotional states, including depression, anxiety and stress to which participants indicate their agreement on a 4-point scale.

Family history of problem drinking: Family history is measured with a subscale taken from the *Addiction Severity Index*⁵⁷. Participants are asked to indicate whether or not four classes of relatives on both their mother’s and father’s side ever “had a significant problem with alcohol or drugs, one that either lead to treatment or should have led to treatment.”

Alcohol-related problems: Participants will complete the long version of the *Young Adult Alcohol Consequences Questionnaire (YAACQ)*, which is comprised of 48 consequences that may have occurred within the past three months.

Alcohol expectancies: The *Comprehensive Effects of Alcohol (CEOA)* measure will be used to assess the extent to which participants report experiencing alcohol-related expectancies (e.g., “After a few drinks of alcohol, I would be more likely to feel dizzy”).

Subjective response to alcohol: An adapted version of the *Self-rating of Effects of Alcohol (SRE; Schuckit et al., 1997*⁹²) will be used at intake to assess the number of alcoholic drinks it took for participants to experience a series of subjective effects (e.g., stimulation, arousal) the first time they drank alcohol, in the past three months and during their period of heaviest drinking. Responses to the adapted SRE will be used to assess self-reported *tolerance* as well. A tolerance score is created by subtracting the score for the first five drinking occasions ($\alpha = .83$) from the score for the recent drinking experiences ($\alpha = .86$)⁹³.

Drinking motives: Drinking motives will be assessed using Cooper and colleagues measure of three types of drinking motives (i.e., social, coping and enhancement or the achievement of pleasurable affect from drinking).

Drinking-induced disinhibition: The *Drinking-Induced Disinhibition Scale*⁶³ (DIDS) is a measure comprised of a series of drinking-related experiences to which participants are asked to indicate agreement on a six-point scale. The DIDS assesses four types of disinhibitory experiences resulting from alcohol use (i.e., euphoric/social, dysphoric, sexual and aggressive).

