Finally, several aspects of the study's methods discourage early departure from the lab, including their acceptance of study-provided transportation to the lab. The pay structure of the study also discourages early departure. We pay participants on an hourly basis during the alcohol drinking sessions, thus persons leaving early would forfeit payment for the remainder of

the session. Any participants who depart early would also forfeit a portion of their pay devoted to adherence to study rules. While there is some benefit to participants in the form of personalized information about their drinking and the opportunity to use smartphone apps designed to facilitate moderate drinking, participants in laboratory studies take part primarily for the monetary compensation, making it unlikely that they will intentionally engage in behaviors that reduce their payment.

Nonetheless, it is possible that a participant could elect to leave the lab early. We have procedures in place should this occur. Study staff will ask individuals who wish to end their participation early to remain in the lab until their breath alcohol reaches the safe level of 0.02% or lower. Study staff will offer these participants transportation by cab to their home, paid for by the study, regardless of whether or not they comply with requests to remain in the lab. Given that participants arrived by cab and will not have a car available, we expect that they will accept study-provided transportation to their home.

During a follow-up phone call on the day after the alcohol drinking session, study staff will verify with participants that they have experienced no adverse events related to the alcohol consumption they engaged in for the study. At a follow-up appointment at the end of the field use period, participants will receive brief counseling and information about their drinking. A master's or doctoral-level clinician will provide participants with a summary of their typical frequency and quantity of alcohol use and related consequences. In addition, treatment referrals will be offered to participants as needed based on their level of drinking and stated concern about their drinking levels. These may include relevant randomized, controlled treatment trials; student health services available at the local colleges and universities along with other local treatment resources. Web-based behavior change options will be offered as well, including NIAAA's "Rethinking Drinking" website.

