Participants may benefit from an awareness of problematic behaviors in which they are engaging, through completion of the interviews and self-reports in this study. They may also benefit from use of the experimental app and moderate their alcohol use. Information about counseling/treatment options will be provided to them as needed. The results of this study could benefit society at large because of the potential public health impact of the proposed app, should it have efficacy in reducing alcohol drinking and related consequences.

9. Conflict of Interest:

None

10. Data Safety and Monitoring Plan:

Designation of Serious Adverse Events:

[name], the PI, has primary responsibility for monitoring the data, assuring protocol compliance, and conducting regular safety reviews after each alcohol drinking session has been completed. [name] will be responsible for distinguishing serious from non-serious adverse events. [name] has sufficient clinical research expertise to make this distinction.

Reporting of Serious Adverse Events

[name] will report serious adverse events in writing within 48 hours to the UF IRB 01 following their policies. The investigator will apprise fellow investigators and study personnel of all adverse events that occur during the conduct of this research project through regular weekly study meetings. An annual report will be submitted to UF IRB 01 summarizing all adverse events.

Female subjects:

Women who are pregnant or nursing, or who report engaging in sexual activity with an opposite sex partner and refuse to use a reliable method of birth control (e.g., condoms +spermicide; birth control pills, diaphragm) will not be allowed to participate in this study. Urine pregnancy tests will be completed at the in-person screening appointment and at an appointment at the research office just prior to alcohol self-administration.

Supervision of Alcohol Administration Sessions:

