The National Advisory Council on Alcohol Abuse and Alcoholism - Recommended Council Guidelines on Ethyl Alcohol Administration in Human Experimentation - Revised May 2005 will be followed. All alcohol drinking sessions will be supervised by [name] herself or by a graduate student or other senior research staff member who will be carefully trained in alcohol self-administration methods and this specific protocol. [name] will either be present at the alcohol drinking session themselves or be readily available on call to make any determination regarding serious versus non-serious adverse events. In addition, the Study Physician [name] will be available for consultation as needed. In cases of illness or injury where medical treatment is needed, the necessary treatment will be provided.

Follow-up:

At a follow-up phone call the day after both alcohol drinking sessions, study staff will verify with participants that they have experienced no adverse events related to the alcohol consumption they engaged in for the study. [name] will review reports of all adverse events interviews. In the case of any medical concerns, participants will be seen by the Study Physician or other medical personnel. Participants will then be directed by these clinicians to obtain further treatment as needed. Participants are screened carefully prior to alcohol administration and all prospective participants who present as psychotic or otherwise severely psychiatrically disabled are excluded, along with those who report psychotropic medication use or a prescription for such medications within the prior 30 days. Given these exclusions, the likelihood of serious psychiatric symptoms arising at this appointment is slight, however if such issues arise, participants will be evaluated immediately by the Study Physician and directed for further treatment as needed. Any Serious Adverse Events that occur during this period will be reported as indicated above.

Procedures for Data Quality Assurance and Confidentiality:

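### No adverse-event or harm instrument is scheduled during field use or at the appointment that closes it, so field-only and EMA participants have no scheduled adverse-event question after screening

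*Combined protocol and SAP*

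**What the plan says.** **Adverse-event form.** The Assessments section says of the SAFTEE that "Adverse experiences are collected on standardized forms". It sits, with the suicidality interview, under the heading "In-Person Screening Appointment and at Preliminary Appointment Day of the Sessions".

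**Next-day call.** Section 10, Follow-up: "At a follow-up phone call the day after both alcohol drinking sessions, study staff will verify with participants" that they had no adverse events from the alcohol consumed for the study. Section 7 describes the same call with the same limit.

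**Safety review.** Section 10 makes the principal investigator responsible for "conducting regular safety reviews after each alcohol drinking session has been completed".

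**End of field use.** The Follow-up appointment section says "After 4 weeks, participants will come to our office for an updated TLFB and give usability and acceptability ratings". An experience interview is added under Assessments. Section 7 adds brief counseling in which a clinician gives a "summary of their typical frequency and quantity of alcohol use and related consequences".

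**Later harm measure.** The 6- and 12-month surveys include the YAACQ, which covers "48 consequences that may have occurred within the past three months".

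**Reporting duty.** Section 10 commits the investigator to written reports of serious events to the IRB within 48 hours, to sharing all adverse events at weekly meetings, and to an annual IRB summary.

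**The concern.** Field use is where participants take the feedback app into their own drinking occasions. For those enrolled only for field use or EMA, it is the whole of their exposure. Yet the scheduled adverse-event questions belong to screening and the laboratory sessions. A duty to report all events does not find them. Without a scheduled question, a low count for field use could mean few events or few reports, and the annual summary could not tell these apart.

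The field-only group also enters under looser criteria. Section 10, Follow-up, argues that serious psychiatric symptoms are unlikely, partly because users of psychotropic drugs and people recently prescribed them are excluded. The footnote to the exclusion criteria waives both of those exclusions for the two field-only scenarios. The exclusion for psychosis or severe psychiatric disability is not waived, so the reassurance is weakened rather than removed.

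**Working it through.** No figure in the plan is in question. The check lists each scheduled contact, what it asks, and whether its window reaches field use.

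| Contact | Adverse-event or harm item listed | Reaches field use? |
|---|---|---|
| In-person or remote screening | SAFTEE, suicidality interview; CARE past-frequency items | No, before app use |
| Web survey linked to screening | YAACQ, past three months | No, looks back from baseline |
| Session-day preliminary appointment | SAFTEE, suicidality interview | No |
| Next-day call | Events related to study alcohol only | No, by its subject |
| Field-only baseline and orientation appointments | None; app set-up, first use and allocation | No |
| Field app prompts and morning entry | None; drinks, drinking time, perceived impairment, wanting and liking more alcohol | Yes, but no harm item |
| EMA surveys | None; drinks, subjective effects, perceived impairment, impaired control, craving, context | Yes, but no harm item |
| 4-week follow-up appointment | No form; drinking calendar, ratings, interview, counseling summary, referrals | Yes, but unstructured |
| EMA closing appointment | None described | Yes, but no harm item |
| 6- and 12-month surveys | YAACQ, past three months | No, see step 2 |

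The drinking calendar (TLFB) helps to read the SAFTEE heading. It sits under the same heading, and the plan says explicitly that it is repeated at the 4-week appointment. It says no such thing of the SAFTEE.

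**Step 1: days after the last scheduled adverse-event contact.** Field use lasts 4 × 7 = 28 days. Assume it starts the day after the last session.
- Laboratory participants: the next-day call falls on day 1 at the latest, leaving 28 − 1 = 27 days. Because the call asks only about study alcohol, even day 1 is covered in name only.
- Field-only participants: no session, so no call and no review triggered by a session. Coverage is 0 of 28 days.
- EMA participants: 0 of 10 days.

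**Step 2: does the YAACQ reach back?** Take three months as about 91 days and six months as about 182. The plan uses two anchors.
- Counted from the session (Exploratory Aim 1): the 6-month window runs from day 182 − 91 = 91 to day 182. Field use ends on day 28, so the gap is 91 − 28 = 63 days.
- Counted from study completion (Six- & 12-month follow ups), taking completion as no earlier than day 28: the window opens at day 28 + 91 = 119. The gap is 119 − 28 = 91 days, about three months.
- The 12-month window covers about months 9 to 12, later still.

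Neither anchor brings field use into a recall window.

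**Step 3: EMA participants.** Their listed payments are $20 + $20 + $30 + $130 = $200, the stated maximum. That leaves nothing for the two $25 follow-up surveys. This suggests, though the plan does not say so, that they do not receive the YAACQ afterwards.

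**The case against.** A reader might infer that harm collection ends with the next-day call. The documents do not support that. The YAACQ is given at 6 and 12 months, 4-week field-only participants complete those surveys, and Exploratory Aim 1 analyzes alcohol-related problems from them. The reporting duties in Section 10 apply to the whole project. At 4 weeks, participants meet a clinician and are interviewed about what they disliked, so events can come up. It would be wrong to say that field events would be absent from the reports by construction; they would depend on being volunteered.

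Nor is the SAFTEE always given before any dosing. The heading refers to sessions in the plural, so a group-day form falls after the dose given at the individual session. Field-only participants are also assessed at screening. Both points stand, but both contacts precede field use.

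Other stronger readings also fail:
- **Share of drinking days uncovered.** Setting field drinking days against laboratory days pools participants' own usual drinking with alcohol supplied by the study. It also needs assumptions about drinking frequency and number of sessions. No such percentage should be quoted.
- **The app as a known hazard.** The plan's warning is conditional: "risk information may increase risky behavior if convenient options are not given". It is given as the reason the app does offer options, so it is not evidence of unmitigated harm.
- **The counseling summary as a contradiction.** The plan does not say which data feed it, and baseline answers could support a summary of typical drinking and consequences.
- **Harms by app-on and app-off block.** No aim asks for this comparison. Splitting a 48-item, three-month instrument into two recalled two-week blocks, with participants aware of which had the app, would be a debatable change to the measure.

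**Conclusion.** The gap is real but bounded. No adverse-event or harm instrument is scheduled during field use or at the appointment that closes it, and later YAACQ windows do not reach back. At least 27 of 28 field days follow the last scheduled adverse-event contact for laboratory participants; all field days do so for field-only and EMA participants. The 27 assumes that field use starts the day after the last session; a later start makes it 28. The YAACQ gap of about 63 to 91 days depends on the survey anchor, but its existence does not.

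The plan does not say how many people will be field-only, apart from a limit of 12 for EMA, so the number affected cannot be given. The finding concerns ascertainment. It does not show that harms occur, and it leaves the primary comparisons and their power unaffected. It is worth correcting because the correction is cheap.

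**What to change.** - Give the SAFTEE, with its window set to the time since last contact, at the 4-week follow-up appointment (in person or by Zoom) and at the EMA closing appointment.
- Extend the principal investigator's safety review and the Follow-up text in Section 10 to these contacts.
- The last sentence of that Follow-up text commits to reporting serious events in a period that it does not define. Define the period so that it includes field use.

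**Cost:** a protocol amendment, a few minutes at contacts that already exist, and more adverse events to record and report. No new visit or instrument is needed. One limit remains: a single question at the end asks participants to recall up to about four weeks, so it will find events late and may miss minor ones.
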